# 7.0 **Reportable Events**

Since all measurement modalities are non-invasive, there are no adverse events anticipated or unanticipated problems involving risk to participants. The risk of the ring adhesive would be minimal as it could chafe the skin when removed.

## 8.0 Study Withdrawal/Discontinuation

Participant can withdraw/discontinue himself or herself from the study. Since the study involves only one visit the process of withdrawal is not effective. However, participants can withdraw the study in any time during the visit.

## 9.0 Statistical Considerations

Five sets of data will be collected from each of the devices and statistical mean and standard error of deviation from the mean will calculated.

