## **Background & Rationale**

Pulse oximeters are commonly utilized medical devices used to measure blood oxygen saturation (SpO2)[2]. These devices (such as the INNOVO Fingertip Pulse Oximeter) are either stand-alone or integrated into physiologic monitoring systems, using 2 wavelengths of lights to determine SpO2. With recent advances in technology, Spatial Frequency Domain Imaging (SFDI) using range of light wavelengths from red to near infrared (NIR) such as in Clarifi(R) (Modulated Imaging, Inc., Irvine CA), smartphones such as Apple Watch (Apple Inc., Cupertino, CA), transcutaneous oximetry TCOM (Perimed Inc., Las Vegas, NV) now have pulse oximetry capabilities. Since it is possible that most patients could utilize this technology, we sought to assess the accuracy, reliability and usability of these oximeters and compare outcomes. In this study, a cohort of 20 healthy volunteers above the age of 18 including males and females of different skin colors will be assessed at the same site and data will be compared. We aim to provide a set of data that will support the clinical and scientific community and identify more than one reliable skin oxygen measurement modalities. The Innovo pulse oximeter device will be used for all subjects.

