#### 1.0 **Objective(s)**

**1.1 Primary Objective** 

To investigate multiplatform for tissue oxygen measurement devices

**1.2** Secondary Objective

To compare other modalities with FDA approved Pulse Oximetry

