## 4.0 Study Design

## 5.0 Enrollment/Randomization

Potential subjects will be identified from IU School of Medicine staff members. Each subject will use all four devices.

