## 6.0 Study Procedures

First the subjects will go through a questionnaire session about their medical history by a designated study team member. The questionnaire data will be placed in RedCap using a subject ID that cannot be linked back to the subject. Then the subject will be consented. Subject will be enrolled. Then the non-invasive data collecting procedure will start on the following equipment:

Spatial Frequency Domain Imaging (SFDI): During consenting period, the Modulim equipment will be calibrated and setup ready for scanning. Subject's volar aspect of the thumb along with the palm surface

will be ready to target the optical camera head. Actual scanning takes less than 60 seconds. The images will be processed offline. During processing 3-5 different regions of interest (ROI) will be taken to measure the oxygen parameters such as tissue oxygen saturation (StO2), oxy-hemoglobin (HbO2), deoxy-hemoglobin (HbR), superficial hemoglobin (HbT1, sub-surface hemoglobin (HbT2). The model used is a Clarifi Modulum

**Transcutaneous oxygen monitoring (TCOM)**: Transcutaneous oxygen monitoring (TCOM or TcpO2) is a noninvasive, clinically-approved method to obtain skin oxygen levels. The method is quantitative, and measures oxygen delivery to the skin from underlying tissue. Before positioning the electrode, an adhesive fixation ring will be placed on the dry skin on the volar aspect of the thumb and an electrolyte as a contact liquid will be filled half and the probe is aligned into it by rotating clock-wise to fasten it. Recording will be started and waited for the oxygen level to stabilize and a fixed value will be recorded. The model used is a Perimed PeriFlux 5000. The probe will be heated to about 45°C. Although this device has other options, only the measurement of  $O_2$  will be performed using this device.

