Statistical Analysis Plan

Protocol Title

Measurement of Oxygen Saturation in healthy human volunteers before, during and after hyperemic events using Multi-Modal Techniques: Spatial Frequency Domain Imaging (SFDI), transcutaneous oxygen measurement (TCOM), Pulse Oximeter, and Apple Watch.

Principal Investigator:

[name]. Assistant Professor, Indiana Center for Regenerative Medicine and Engineering at Indiana University Department of Surgery, Division of Plastic Surgery School of Medicine, Indiana University Analysis will be performed based on search of answers for the questions designed.

Q1: What are the correlations between the measurements we've taken? Are those correlations significant?

The repeated measures correlations for the measurements. Use repeated measures correlation because we have repeated measures for our data (we get values for each measurement four separate times).

Q2: What are the differences between males' and females' measurements, over time?

We have 20 subjects (13 male, 7 female). We have 5 parameters for each subject: StO2, HbO2, HbR, HbT1, and HBT2. Each measurement will be recorded at 4 time points: baseline, occlusion, reactive hyperemia, and recovery. Plots showing how subjects' measurements changed over time will be obtained. The mean measurement value for males and females, over time will be obtained. Hypothesized that males' and females' measurements follow similar patterns over time. StO2 for males will have higher average HbO2, HbR, HbT1 and HbT2 measurements than females, over all time points compared to females.

Q3. Is this male/female gap in measurements statistically significant, though?

To answer this, I fit multivariate linear regression models at each time point. Results of multivariate linear regression models, for each time point will be obtained. Multivariate models are basically just regression models with multiple outcome variables; in this case, the outcomes are the 5 measurements. The regression coefficients for the intercepts are basically the estimated average measurement for males, for that measurement, at that time point; the p values for the intercepts don't really matter. The regression coefficients for female is just the estimated average difference between males and females, for that measurement, at that time point.

Example:

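### Section 9.0 gives each device only a mean and standard error of five undefined data sets, so the Background's reliability aim has no statistic that answers it

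*Protocol*

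**What the plan says.** Section 9.0 of the Protocol (Statistical Considerations) reads in full: "Five sets of data will be collected from each of the devices and statistical mean and standard error of deviation from the mean will calculated". It does not say whether a set is a repeat reading, a region of an image, a study phase or something else. It does not say whether the mean and SE are taken within a subject, across subjects or over all readings. Its wording also leaves open whether an SD or an SE is intended.

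The Background gives the purpose: "we sought to assess the accuracy, reliability and usability of these oximeters and compare outcomes", in "a cohort of 20 healthy volunteers above the age of 18". Section 1.2 adds the secondary objective: "To compare other modalities with FDA approved Pulse Oximetry". Section 5.0 fixes the design: "Each subject will use all four devices".

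Section 6.0 describes the readings. For SFDI, "During processing 3-5 different regions of interest (ROI) will be taken to measure the oxygen parameters". For TCOM, the operator "waited for the oxygen level to stabilize and a fixed value will be recorded". Measurements are taken in three phases: baseline, cuff occlusion, and after release.

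The SAP's title names all four devices. Its listed outcomes are five SFDI parameters (StO2, HbO2, HbR, HbT1, HbT2) at four time points, analysed by repeated measures correlation and by a regression at each time point.

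**The concern.** Reliability asks how closely a device repeats itself on the same person under the same conditions. That is a question about within-subject variation. An SE describes how precisely a mean is known, and it shrinks as readings or subjects are added. A plan that reports only a mean and SE may therefore hold the data needed for the reliability question and still not answer it.

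The second issue is the unit of analysis. Readings on one person are likely to be correlated. If five readings from each of 20 people were treated as 100 independent values, the SE of a device mean would be too small. Section 9.0 does not say whether this is intended.

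The SAP does not fill the gap. Its first question, on correlations among the measurements taken, could be read to include other devices, but its closing summary refers to the five SFDI measurements. Correlation is in any case neither agreement nor repeatability.

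**Working it through.** **Inputs.** Subjects n = 20 (Protocol, Background; SAP, 13 male and 7 female). Data sets m = 5 (Protocol 9.0). The documents give no ICC, so it is assumed and its range from 0 to 1 is shown. For steps 3 to 5, the five sets are taken to be repeats within a subject, which is also an assumption.

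**1. The plan's own figures.** There is no stated SE, power or sample-size basis to reproduce. The only inferential figures are the SAP's two worked examples, checked here as 20 subject-level values in two groups (18 degrees of freedom, t = 2.101):
- Sex difference 4, CI -11 to 19: SE = 15/2.101 = 7.14, p = 0.582 (stated 0.581).
- Skin-type difference -20, CI -33 to -7: SE = 13/2.101 = 6.19, p = 0.0046 (stated 0.004, within the rounding of the estimate and CI).

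Both are consistent with one value per subject. The rounded figures do not prove it, and they concern SFDI only.

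**2. What are the five sets?** Five matches neither the three phases in Protocol section 6.0 nor the four SAP time points. SFDI takes 3 to 5 regions of interest, which is a possible but unconfirmed source. TCOM is described as giving one stabilised value per recording.

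**3. Can a mean and SE show reliability?** Take the SE across subject means, with total variance scaled to 1:

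SE² = [ICC + (1 - ICC)/5]/20, and within-subject variance = 1 - ICC.

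Hold the SE at 1.0. The within-subject SD is then sqrt{(1 - ICC) × 20/[ICC + (1 - ICC)/5]}:
- ICC 0.2: sqrt(0.8 × 20/0.36) = 6.67
- ICC 0.5: sqrt(0.5 × 20/0.60) = 4.08
- ICC 0.9: sqrt(0.1 × 20/0.92) = 1.47

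Over pooled readings the same problem arises. An SE of 1.0 from 100 readings means a total SD of about 10, so the within-subject SD is 10 × sqrt(0.8) = 8.94 at ICC 0.2 and 10 × sqrt(0.1) = 3.16 at ICC 0.9. Either way, one SE fits devices of very different repeatability.

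**4. SE of a device mean if 20 × 5 = 100 readings are pooled.** The pooled SE is SD/sqrt(100). The correct SE is SD × sqrt{[ICC + (1 - ICC)/5]/20}. Their ratio is sqrt(1 + 4 × ICC).

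| Assumed ICC | Correct SE / pooled SE | Simulated coverage of the pooled 95% CI |
|---|---|---|
| 0 | 1.00 | not simulated |
| 0.3 | 1.48 | 81% |
| 0.5 | 1.73 | 73% |
| 0.75 | 2.00 | 66% |
| 0.9 | 2.14 | 63% |
| 1.0 | 2.24 | not simulated |

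Coverage is from 20,000 simulated studies per row. With one mean per subject, coverage was about 95% throughout, and the SE is not understated.

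**5. SE over one subject's five readings.** This is the within-subject SD divided by sqrt(5). It exceeds the correct group SE when (1 - ICC)/5 > [ICC + (1 - ICC)/5]/20. That reduces to 3.8 > 4.8 × ICC, or ICC below about 0.79.

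**The case against.** The strongest reply is that section 9.0 never says readings are pooled. Taking the SE across 20 subject means is just as natural, and then nothing is understated. The SAP's worked examples, the only evidence of how the analyst works, fit subject-level values. This stands: the pooling error is a possibility left open, not a planned fault.

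A reader might infer that the device SEs will be about half their proper size. The documents do not support that. It needs both pooling and an ICC of roughly 0.6 or more (factor 1.84 at 0.6), and neither is stated.

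A reader might also infer that devices will falsely appear to differ. That is not established either. All four devices are used on each subject, so contrasts are paired. For devices on the same scale with equal variances, the correct paired SE divided by the pooled unpaired SE is sqrt[1 + ICC × (4 - 5r)], where r is the assumed correlation of subjects' true values between devices. At ICC 0.8 this is 2.05 for r = 0, 1.48 for r = 0.5 and 1.00 for r = 0.8. For larger r the naive SE is too large. Section 9.0 plans no test between devices in any case.

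Two further replies are fair. If the SE were taken over one subject's five true repeats, multiplying it by sqrt(5) would recover a repeatability SD, so the criticism in step 3 applies to an SE across subjects or over pooled readings. And reliability appears in the Background, not among the numbered objectives or outcomes. It is still a declared purpose of the study, and the Background also aims to identify more than one reliable modality.

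**Conclusion.** The point holds in this form: section 9.0 leaves the five data sets and the unit of analysis undefined, and neither document specifies a statistic for reliability. For TCOM, the pulse oximeter and the watch, section 9.0 is the only analysis rule.

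That a mean and SE, across subjects or over pooled readings, cannot separate a repeatable device from a poor one does not depend on any particular ICC. The assumed ICCs serve only to show the size of the gap: a within-subject SD of 6.67 against 1.47 for the same SE.

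The understatement of the SE is conditional. It runs from none to a factor of 2.24 if 100 readings are pooled as independent, and is absent if subject means are used. No direction of error can be claimed for device comparisons. This should be corrected, but it does not show that any reported result is wrong.

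**What to change.** - State what the five sets are: repeats per subject, device and phase, or otherwise. This comes first, because the rest depends on it.
- State whether SD or SE is meant.
- Make the subject the unit of analysis, using subject means per device and phase or a mixed model with a random subject effect, with confidence intervals over the 20 subjects.
- Where true repeats within a phase exist, report within-subject SD, repeatability coefficient and ICC for each device as the reliability result.
- Where a device has one reading per phase, state that its repeatability cannot be estimated. Regions within one SFDI image should not be presented as repeat measurements without justification.
- Compare devices as paired within subject.

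The cost is revised wording, a small variance-components analysis and possibly wider error bars. The SAP already reports estimates, so new wording cannot supply repeats that were never recorded. For those devices the change is an explicit limitation.

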## **10.0** Statistical Data Management

Primary data will be collected via direct data measurement and imaging, whichever applies to the devices. TCOM, Pulse oximeter and apple watch date will be recorded with pen & paper and entered on the spread sheet and stored electronically in REDCap. The storage location will be backed up manually for every subject and at the end of the subject visit. The quality control methods will be used single entry with random checks of accuracy.

## **11.0 Privacy/Confidentiality Issues**

Regarding the method for ensuring participant privacy and for protecting privacy and confidentiality, each subject will be given a subject ID and only non-identifiable demographic data will be collected. Data will be stored on REDCap and access will be limited to designated personnel who processes the data.

## 12.0 Follow-up and Record Retention

The duration of the data collection will be 1-2 hours and the study will be within 6 months. The duration of record retention will be for 5 years and after that destruction or the possibility of indefinite archiving of information.

Statistical Analysis Plan

Protocol Title

Measurement of Oxygen Saturation in healthy human volunteers before, during and after hyperemic events using Multi-Modal Techniques: Spatial Frequency Domain Imaging (SFDI), transcutaneous oxygen measurement (TCOM), Pulse Oximeter, and Apple Watch.

Principal Investigator:

[name]. Assistant Professor, Indiana Center for Regenerative Medicine and Engineering at Indiana University Department of Surgery, Division of Plastic Surgery School of Medicine, Indiana University Analysis will be performed based on search of answers for the questions designed.

Q1: What are the correlations between the measurements we've taken? Are those correlations significant?

The repeated measures correlations for the measurements. Use repeated measures correlation because we have repeated measures for our data (we get values for each measurement four separate times).

Q2: What are the differences between males' and females' measurements, over time?

We have 20 subjects (13 male, 7 female). We have 5 parameters for each subject: StO2, HbO2, HbR, HbT1, and HBT2. Each measurement will be recorded at 4 time points: baseline, occlusion, reactive hyperemia, and recovery. Plots showing how subjects' measurements changed over time will be obtained. The mean measurement value for males and females, over time will be obtained. Hypothesized that males' and females' measurements follow similar patterns over time. StO2 for males will have higher average HbO2, HbR, HbT1 and HbT2 measurements than females, over all time points compared to females.

Q3. Is this male/female gap in measurements statistically significant, though?

To answer this, I fit multivariate linear regression models at each time point. Results of multivariate linear regression models, for each time point will be obtained. Multivariate models are basically just regression models with multiple outcome variables; in this case, the outcomes are the 5 measurements. The regression coefficients for the intercepts are basically the estimated average measurement for males, for that measurement, at that time point; the p values for the intercepts don't really matter. The regression coefficients for female is just the estimated average difference between males and females, for that measurement, at that time point.

Example:

For StO2 at time 1, it's estimated that males have an StO2 value of 62, with a 95% confidence interval of 54 to 70. It's estimated that females have StO2 values at time 1 that are 4 higher than males, on average [95% confidence interval ranges from 11 lower than males, to 19 higher than males]. That confidence interval [-11 to 19] contains 0, so there's a strong enough possibility that the difference between male and female StO2 values at time 1 is 0 (i.e. there's no difference). Because of that, the p value for Time 1/StO2/Female is 0.581, which is greater than .05, which

means we can't reject the idea the females and males have the same StO2 values at time 1.

Q2: Instead of gender, what about differences between skin type (II and III vs. IV)?

Plot of measurements over time for subjects with skin type II and III vs. skin type IV will be analyzed. The data represent the mean measurement value for skin types 2 and 3 vs skin type 4, over time. Based on the above plots, it appears that (on average) those with skin type 4 have lower StO2 and HbO2 over time, compared to those with skin type 2 and 3. Skin type 4s appear to have higher HbR and HbT1 over time, compared to skin type II and III. There's a lot of variation in HBT2 over time, and both skin type groups have similar mean values over time. Like for gender, I fit separate multivariate linear regression models for each time point. The regression coefficients for the intercepts are basically the estimated average measurement for the skin type II + III group, for that measurement, at that time point; the p values for the intercepts don't really matter. The regression coefficients for skin type IV is just the estimated average difference between 4s and 2s + 3s, for that measurement, at that time point.

Example:

For StO2 at time 1, it's estimated that type 2s and 3s have an StO2 value of 71, with a 95% confidence interval of 63 to 78. It's estimated that type 4s have StO2 values at time 1 that are 20 lower than type 2s and 3s, on average [95% confidence interval ranges from 33 lower than 2s and 3s, to 7 lower than 2s and 3s]. That confidence interval [-33 to -7] does not contain 0, meaning we're confident that the difference between 4s and 2s/3s is not 0. Because of that, the p value for Time 1/StO2/Female is 0.004, which is less than .05, which means we can reject the idea that 4s and 2s/3s have the same StO2 values at time 1. Most of the 5 measurements are correlated with one another. Females and males had similar measurements at baseline, but started to differ in HbO2, HbR, HbT1, and HbT2 from inflation onwards. Those with skin type 4 had lower StO2, higher HbR, and higher HbT1 compared to those with skin type 2 and 3, at all-time points; the two groups didn't significantly differ in regard to HbO2 and HbT2 at any time.

Abbreviation StO2= tissue oxygen saturation HbO2=oxy hemoglobin HbR= deoxy hemoglobin HbT1= superficial perfusion hemoglobin HbT2= deep perfusion hemoglobin TCOM=trans-cutaneous oxygen measurement

SFDI=spatial frequency domain imaging

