  - b) Occlusion of the blood flow using pressure cuff at 200mmHg for 2 minutes and then collect the data during occlusion. There is a minimal risk of pain on the arm inflation of the pressure cuff up to 200mmHg. Please see literature (1) where they have used 240mmHg.
  - c) Releasing the cuff and collecting the data during the hyperemic phase (post-deflation of the cuff).

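### SAP Q1 tests correlations against zero over the cuff phases with no phase term, so significance cannot separate parameters that track each other from a shared cuff response, and two StO2 pairs are probably correlated by construction

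*SAP*

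**What the plan says.** The SAP's first question is "Q1: What are the correlations between the measurements we've taken? Are those correlations significant". The method is repeated measures correlation, and the only justification is the number of repeats: "Use repeated measures correlation because we have repeated measures for our data (we get values for each measurement four separate times". No phase term, treatment of derived parameters or multiplicity rule is given.

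Q1 does not list its variables, but the next question does: "We have 5 parameters for each subject: StO2, HbO2, HbR, HbT1, and HBT2". All five appear in the protocol (6.0 Study Procedures, SFDI) as outputs of the SFDI images, beginning with "tissue oxygen saturation (StO 2 ), oxy-hemoglobin (HbO 2 ), deoxy-hemoglobin (HbR". The repeats are the stages of an imposed challenge: "Each measurement will be recorded at 4 time points: baseline, occlusion, reactive hyperemia, and recovery". The protocol describes the challenge as "Occlusion of the blood flow using pressure cuff at 200mmHg for 2 minutes and then collect the data during occlusion", followed by release.

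The SAP's closing conclusions already answer Q1: "Most of the 5 measurements are correlated with one another". No coefficient, p-value or interval accompanies the statement.

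**The concern.** Zero is a useful reference value for a correlation only if unrelated quantities would be expected to give zero. That is doubtful here for two separate reasons.

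- **Derivation.** The SAP's abbreviation list defines StO2 as a tissue oxygen saturation and lists it beside oxy- and deoxy-haemoglobin. A saturation is ordinarily the oxygenated share of the two. If StO2 is computed that way, testing it against its own components mostly tests the formula.
- **Common driver.** Repeated measures correlation removes each subject's mean. It does not remove a shift that every subject undergoes at the same phase. Two parameters that respond to the cuff in a similar or mirrored way therefore carry a common pattern into the coefficient, even if they are unrelated within a phase.

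At stake is how the answer to Q1 is read. A significant result would be taken to show that the parameters track each other, when it may show only that both respond to an inflated cuff. The derivation problem also affects the skin-type conclusions, which list lower StO2 and higher HbR as if they were separate evidence.

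**Working it through.** **Inputs from the documents.** There are 20 subjects ("We have 20 subjects (13 male, 7 female"), 4 time points, and 5 parameters, giving 5×4/2 = 10 pairs. The level of 0.05 is taken from the SAP's worked examples, because Q1 states none. Q1 prints no coefficient or p-value, so there is no figure to reproduce.

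**Assumptions, not in the documents.** The StO2 formula, the size and shape of the cuff response, and the within-subject variation are all assumed.

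**Reference value.** Degrees of freedom are N(k-1)-1 = 20×3-1 = 59, so |r| must exceed 0.252 for two-sided p < 0.05. The protocol's visit sequence lists three phases, not four. With three, df = 20×2-1 = 39 and the threshold is about 0.31; the argument is unchanged.

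**Check 1: the derived pairs.** HbO2 and HbR were simulated as independent with no cuff effect, and StO2 was set to 100×HbO2/(HbO2+HbR). There were 5,000 data sets per setting, with StO2 centred at 60% to 75% and a within-subject CV of 5% to 20%, the same for both haemoglobins.

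- StO2 with HbO2: mean r 0.67 to 0.69, rejected in 100% of runs.
- StO2 with HbR: mean r -0.70, rejected in 100%.
- HbO2 with HbR: about 5% rejected, as it should be.
- With phase means removed, the first two results do not change.

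A first-order calculation agrees. Small changes in StO2 are proportional to the proportional change in HbO2 minus that in HbR. With independent CVs a and b, r(StO2,HbO2) ≈ a/√(a²+b²) and r(StO2,HbR) ≈ -b/√(a²+b²). For a = b these are ±1/√2 = ±0.71. With unequal CVs the split changes: at b = 4a they are 1/√17 = 0.24 and -4/√17 = -0.97. The squares always sum to about 1, so at least one of the two is 0.71 or more in size.

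**Check 2: the shared cuff response.** Two parameters with independent within-phase residuals (SD 1) were given the profile (0, -s, +s, 0) over the four phases. Per subject, the profile contributes 2s² to the centred cross-product, and the residuals contribute 3 to each sum of squares, so the expected r ≈ 2s²/(2s²+3).

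| s (within-phase SD) | Formula r | Simulated r | Rejected, no phase term | Rejected, phase means removed |
|---|---|---|---|---|
| 0 | 0 | 0.00 | 5% | 5% |
| 0.25 | 0.125/3.125 = 0.04 | 0.04 | 6% | 5% |
| 0.5 | 0.5/3.5 = 0.14 | 0.14 | 20% | 5% |
| 1 | 2/5 = 0.40 | 0.40 | 92% | 5% |
| 2 | 8/11 = 0.73 | 0.73 | 100% | 5% |

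The adjusted analysis has (20-1)×3-1 = 56 df. Other profiles gave the following:

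- Mirror-image profiles: nearly the same rejection rates, with negative r.
- Partial overlap (the second parameter responds only to occlusion, or only to hyperemia): 44% at 1 SD, about 89% at 1.5 SD, over 99% at 2 SD.
- Only one parameter responds: about 5% at every s.
- Orthogonal profiles, (0, -s, +s, 0) against (0, +s, +s, 0): 1% to 5%.

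**The case against.** The cuff is the intended challenge, and the study title is about oxygenation before, during and after it. Whether the parameters move together across the manoeuvre is a fair descriptive question, and unadjusted repeated measures correlation answers it. Adjusting for phase answers a different question, whether subject-specific deviations go together, and with one value per phase those deviations may be largely noise. This stands. It is a reason to report both coefficients and label each, not to discard the unadjusted one.

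The inflation is also conditional. It requires profiles that overlap or mirror each other, and the documents give neither sizes nor shapes. A reader might infer that any two parameters that respond to the cuff must correlate, or that the SAP's conclusion was guaranteed in advance. The orthogonal case above shows the first is false. The second is not shown either: the formula accounts for 2 of 10 pairs, and the rest depends on unreported profiles.

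A reader might also infer that all five parameters are algebraically linked. Nothing in the documents makes HbT1 or HbT2 a function of the others, and HbO2 and HbR are not forced to correlate.

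Finally, the SAP omits multiplicity. Ten independent tests at 0.05 would give at least one false positive with probability 1-0.95^10 = 40%. That is a separate weakness, and phase adjustment does not cure it.

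**Conclusion.** The point holds in a limited form. Tested against zero with no phase term, a significant correlation among these parameters does not show association beyond the common response to the cuff. For StO2 with HbO2 and with HbR, it may show little more than how StO2 is computed.

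The result for those two pairs rests on the standard saturation formula. The symmetric ±0.7 also rests on similar proportional variation in HbO2 and HbR. For the other eight pairs, the size depends on the unknown cuff response: negligible at 0.25 SD, about 20% false significance at 0.5 SD and above 90% at 1 SD for identical profiles, and none for a single responder or orthogonal profiles.

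On skin type, a reader might infer that lower StO2 and higher HbR are one observation reported twice. The documents do not support that. It would need equal HbO2 in the two groups. The SAP's conclusions report only no significant difference in HbO2, and its skin-type section says HbO2 appears lower in type IV. For the same reason, the StO2 example cannot be converted into an HbR ratio. The two findings are linked, so they are not independent evidence, but they are not identical.

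Severity is minor to moderate. Q1 feeds no stated endpoint or decision, but its answer already stands as a conclusion.

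**What to change.** 1. State in the SAP how the device computes StO2. If it is derived from HbO2 and HbR, say so, take the StO2-HbO2 and StO2-HbR pairs out of the significance tests, and show them descriptively.
2. For the other eight pairs, report two coefficients side by side: the unadjusted repeated measures correlation, labelled as co-variation across the cuff manoeuvre, and one with time point as a factor. Base any claim of association beyond the manoeuvre on the second.
3. Reword the closing statement on correlations to match. Describe lower StO2 and higher HbR by skin type as linked findings, neither as independent results nor as the same observation.

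The cost is SAP wording and one extra model term on data already collected. The adjusted correlations may be smaller and noisier, and fewer are likely to be significant. Phase adjustment does not repair the two StO2 pairs, so step 1 is needed as well as step 2.
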